## **8.0 PRETREATMENT EVALUATION**

The following tests and procedures are required prior to protocol registration. These procedures are standard of care.

Within 4 weeks prior to registration

- Physical examination
- ECOG performance status
- Vital signs (weight, heart rate, blood pressure, respiratory rate, oxygen saturation) will be assessed in clinic
- Complete blood count (CBC)
- Comprehensive metabolic profile (CMP)
- Hepatitis B and C panels (Hepatitis B Surface Antigen, Hepatitis B Core Antibody (total), Hepatitis B Surface Antibody, Hepatitis C Antibody), and possible additional testing, depending on serological testing
- Prothrombin and activated partial thromboplastin time test (PT&APTT)
- Clinical review of the MSK histopathology report confirming cancer
- Quality of life assessment (Skindex -16, Appendix B) will be completed by subjects
- Pregnancy test for women of childbearing potential (by either blood or urine)
- Digital photography will be performed to document the location and size of cutaneous metastases.
- PET/CT (IV or oral contrast is not required, but is permissible if clinically indicated.)

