## **End of Treatment**

Week 16 ( $\pm$  1 week) or when TVEC is discontinued prior to week 15

- Physical examination
- ECOG performance status
- Vital signs (weight, heart rate, blood pressure, respiratory rate, oxygen saturation) will be assessed in clinic
- Adverse event review (including NCI PRO-CTCAE v1.0, Appendix C)
- Complete blood count (CBC)
- Comprehensive metabolic profile (CMP)
- Prothrombin and activated partial thromboplastin time test (PT&APTT)
- Research blood test (If TVEC stopped before week 15)
- Pregnancy test for women of childbearing potential (by either blood or urine)
- Research skin tumor biopsy (If TVEC stopped before week 15)
- Quality of life assessment (Skindex-16, Appendix B) to be completed by subjects
- Digital photography
- PET/CT (IV or oral contrast is not required, but is permissible if clinically indicated.)

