## 10.0 EVALUATION DURING TREATMENT/INTERVENTION

Study Timeline	Pre-Treatment	Treatment									End of Treatment 	Follow-Up 
		0 (1)	3 (1)	5 (1)	7 (1) 	9 (1)	11 (1)	13 (1)	15 (1)	16 (1)		
Week (+/-)	-4 to 0											
Assessments												
Pathology Review	X											
PET/CT (with or without contrast)	X									X		
Quality of life questionnaires	X									X		
Digital photography	X									X		
Adverse event		X	X	X	X	X	X	X	X	X		X

review 											
ECOG performance status	X	X	X	X	X		X		X	X	
Vital signs (weight, heart rate, blood pressure, respiratory rate, oxygen saturation)	X	X	X	X	X		X		X	X	
Physical exam	X	X	X	X	X		X		X	X	
Complete medical history	X										
Hepatitis B Surface Antigen, Hepatitis B Core Antibody (total), hepatitis B surface Antibody, Hepatitis C Antibody 	X										
Comprehensive metabolic profile	X									X	
Basic metabolic profile		X	X	X	X		X		X		
Complete blood count	X	X	X	X	X		X		X		
PT&APTT	X	X	X	X	X		X		X		
Pregnancy testing (blood or urine); WOCBP only	X 		X		X		X		X		
Research blood test 		X	X	X	X		X		X		
Research skin punch biopsy 		X			X				X		
Treatment											
TALIMOGENE LAHERPAREPVEC		X	X	X	X	X	X	X	X†		
Radiation therapy			X*								

†Patients with potential for clinical benefit may continue TALIMOGENE LAHERPAREPVEC after week 15 every 2 weeks for up to 24 weeks (as determined by treating clinician)

\*Only for Arm A; first fraction given 6 (+/- 2) hours after week 3 TALIMOGENE LAHERPAREPVEC administration; 2nd and 3rd fraction given every 3-6 days over no more than 14 days

Including Appendix C, "NCI PRO-CTCAE v1.0"

Within 2 weeks of starting Talimogene Laherparepvec treatment

 Research bloods will be 3 tubes (3 CPT) at each time point; stored at immune monitoring core facility for up to 1 year after completion of study

One lavender top (EDTA) tube of blood will be drawn on the same day as the research skin punch biopsy; window for biopsy will be +/- 3 weeks

Additional testing to evaluate for hepatitis maybe required depending on the serological results

For patients that discontinue TVEC before week 16, the End of Treatment visit occurs after last dose of TVEC

Follow-Up at week 20 or 4 weeks after last TVEC dose

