Patient reported health-related quality of life outcomes will be assessed using the Skindex-16 (Appendix B). The Skindex-16 is a 1 page instrument consisting of 16 items with responses provided on a 7-point Likert scale based on experience over the last week. Responses are categorized in 3 subscales: emotions, functioning, and symptoms, with combined subscale scores yielding an overall score ranging from 0 (best) to 100 (worst). Of the 16 items in the instrument, 7 contribute to symptoms, 4 contribute to emotion, and 5 contribute to functioning. In a psychometric analysis, subscales have a high degree of internal consistency reliability (Cronbach's alpha = 0.86, 0.93, 0.92 for symptoms, emotions and functioning). The subscale scores were also highly reproducible after 72 hours ( $r= 0.90, 0.89, \text{ and } 0.88$  for symptoms, emotions and functioning) (Chren MM J Cutan Med Surg 2001).

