## **13.0 CRITERIA FOR REMOVAL FROM STUDY**

Consent for participation in the study may be withdrawn by the patient or patient's health care proxy at any time.

If at any time, the patient develops clinically significant progressive disease, s/he will be withdrawn from the study and referred for alternative therapy.

If at any time the patient is found to be ineligible for the protocol as designated in the section on Criteria for Subject Eligibility (i.e., a change in diagnosis), the patient will be removed from the study.

If at any time, the protocol therapy jeopardizes the safety of the patient, s/he may be withdrawn from the study.

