## **14.0 BIOSTATISTICS**

Patients will be randomized into two separate arms (stratified by disease type), each of which will use a Simon's optimal two-stage design to assess the primary endpoint of systemic response (defined as patients achieving partial response or complete response) of a metastasis that was not injected or irradiated. The single largest measurable metastatic disease site will be used for this assessment 16 weeks after the first dose of Talimogene Laherparepvec. For each arm, a 7.5% or lower response rate is considered not promising, a 27% or higher response rate is considered promising, and the probabilities of a type I error (falsely accepting a non-promising therapy) and type II error (falsely rejecting a promising therapy) are set to 0.10 and 0.20, respectively.

In the first stage, 9 evaluable patients will be accrued to each arm. If at least 1 patient achieves response among these 9 patients, then an additional 6 patients will be accrued to that arm in the second stage. If no patients achieve response then that arm will be closed to further accrual and declared negative. At the end of the trial if 3 or more patients achieve response out of 15 then that treatment arm will be considered worthy of further investigation. This design has an early stopping probability of 0.06 if the true response rate is at least 27% and 0.50 if the true response rate is at most 7.5%. Although a comparison will be done between the two arms by a two-sample proportion test on response rates, this sample size may not have enough power to distinguish the two arms. Thus if both treatment arms are declared worthy of further investigation compared to historical control rate, the treatment arm with the higher observed response rate will be selected as the preferred treatment modality for future studies. The probabilities of selecting correctly the arm with the true higher response rate are given below. The maximum number of patients needed is 30, for which we expect to enroll in 36 months.

True response rates for the two arms	27% vs 35%	27% vs 40%	27% vs 45%	30% vs 35%	30% vs 40%	35% vs 40%	35% vs 45%	35% vs 50%
Probability of picking the correct arm (i.e., the one with the higher response rate)	0.61	0.72	0.80	0.54	0.65	0.54	0.65	0.74

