Note that in the above, all patients are assumed evaluable. However, it might happen that some patients are not evaluable due to various reasons such as withdrawal or loss to follow-up, etc. Such inevaluable patients will be replaced. We expect that about 13% of patients might need to be replaced. In other words, we expect to enroll up to 34 patients in total. The clinical efficacy of Talimogene Laherparepvec will be measured by the ORR and summarized by the sample proportion for each of the two arms. A comparison will be done between the two arms. Safety of Talimogene Laherparepvec will be summarized and compared similarly. QOL total and subscale scores will be summarized numerically and graphically, and trends will be observed and reported per arm. Wilcoxon rank sum tests will also be used to compare the QOL scores between the two arms for each assessment time point. DOR will be assessed using actuarial curves based on patients who achieved response and compared between the two arms using a stratified log-rank test. Time to response onset, progression free and overall survival will be analyzed in a similar way but will be based on all patients. Immunologic response data will be summarized descriptively, with mean, median and standard deviations calculated.

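### Skindex-16 is compared between arms by unadjusted rank-sum tests at baseline and at week 16: the baseline test says nothing about treatment, and the valid week-16 test leaves the baseline score unused

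*Combined protocol and SAP*

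**What the plan says.** Section 14.0 gives two sentences to quality of life. The first is descriptive: "QOL total and subscale scores will be summarized numerically and graphically, and trends will be observed and reported per arm". The second is the between-arm test: "Wilcoxon rank sum tests will also be used to compare the QOL scores between the two arms for each assessment time point". It names no baseline covariate, change score or stratification.

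The schedule fixes what the time points are. Section 8.0, which lists what must be done before registration, includes "Quality of life assessment (Skindex -16, Appendix B) will be completed by subjects". The end-of-treatment list in Section 9.0 (week 16, or earlier if the injections stop before week 15) includes "Quality of life assessment (Skindex-16, Appendix B) to be completed by subjects". In the Section 10.0 table the row "Quality of life questionnaires" is marked at pre-treatment and at week 16 only. Section 15.2 places randomisation after eligibility and registration, so the first score always precedes randomisation.

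Section 12.0 describes three subscales and an overall score from 0 (best) to 100 (worst). Secondary objective 3 in Section 2.0 expects quality of life to improve after treatment. No alpha, power or target difference is given for Skindex-16.

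**The concern.** With only two time points, testing at each of them includes a test at baseline. Under proper randomisation any baseline difference between the arms is chance. A significant result there carries no information about treatment, and a non-significant one does not show that the arms are balanced.

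The week-16 test treats the second score as if the first did not exist. Both come from the same patient on the same scale, so they are probably correlated. Adjusting for the first removes part of the patient-to-patient variation. It also deals, by a rule fixed in advance, with a chance imbalance in arms of 15, or of 9 if an arm closes at stage 1. As written, a visible baseline imbalance would leave the team either to ignore it or to adjust after seeing the data.

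At stake is the precision of one secondary comparison. The primary endpoint and the Simon rule are untouched.

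**Working it through.** **Inputs from the documents.** Two Skindex-16 assessments (Sections 8.0, 9.0, 10.0); an unadjusted rank-sum test (Section 14.0); 9 evaluable patients per arm at stage 1 and 15 at the end (Section 14.0).

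**Assumptions, not in the documents.** Correlation rho between baseline and week-16 scores of 0.3, 0.5 or 0.7; a between-arm difference of 0.3, 0.5 or 0.8 SD; normal scores; complete pairs; two-sided 0.05.

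**1. The plan's own figures.** None exists for quality of life. The arm sizes come from the Simon design, and its figures reproduce. Early stopping is (1 - p)^9: 0.925^9 = 0.496 and 0.73^9 = 0.059, against the stated 0.50 and 0.06. Exact type I error is 0.094 (limit 0.10) and power 0.802 (target 0.80).

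**2. What adjustment buys in principle.** Adjusting for baseline multiplies the variance of the arm difference by 1 - rho²: 0.91, 0.75 and 0.51. With large-sample rank-sum efficiency 3/pi, the difference detectable with 80% power at 15 per arm is (1.960 + 0.842) × sqrt(2 / (15 × 0.955)) = 1.05 SD without baseline. Multiplying by sqrt(1 - rho²) gives about 1.00, 0.91 and 0.75 SD.

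**3. Simulated power, 15 per arm.** Rank-sum uses the normal approximation with continuity correction. Rank ANCOVA regresses the week-16 rank on arm and baseline rank. There were at least 20,000 trials per setting, so the figures are good to about 0.01.

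| Difference | Rank-sum | Rank ANCOVA, rho 0.3 / 0.5 / 0.7 |
|---|---|---|
| 0.8 SD | 0.52 | 0.57 / 0.63 / 0.77 |
| 0.5 SD | 0.24 | 0.26 / 0.30 / 0.41 |
| 0.3 SD | 0.11 | 0.13 / 0.14 / 0.17 |
| 0.8 SD, about 38% of baseline scores at the best value (assumed) | 0.44-0.45 | 0.47 / 0.52 / 0.62 |

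The last row matters because the scale is bounded and ties at the floor are plausible. Skewing the scores by a monotone transformation would test nothing, since it leaves the ranks unchanged. At rho 0 the two tests have practically the same power (0.52-0.53 at 0.8 SD).

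**4. Smaller arms, 0.8 SD.** With 15 against 9: 0.41 against 0.44/0.50/0.63. With 9 per arm: 0.31 against 0.35/0.40/0.51. At 9 per arm, about 0.03 of that gain is only the conservatism of the rank-sum test, because rank ANCOVA already reaches 0.33 at rho 0.

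**5. Validity.** With no true difference the rank-sum test rejects in about 4.5% of trials at 15 per arm and 4% at 9; rank ANCOVA rejects in about 5%.

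**6. Chance imbalance.** At 15 per arm the SD of the baseline mean difference is sqrt(2/15) = 0.365, so a difference above 0.5 SD has probability 2 × (1 - Φ(0.5/0.365)) = 0.17. With no treatment effect, the unadjusted test rejects in about 7%/10%/16% of those trials and in about 4%/3%/2% of the rest; rank ANCOVA stays near 5% in both. This ignores stratification by disease type. If disease type predicts the score, 17% is somewhat too high.

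**The case against.** The strongest reply is that the planned test is valid, the endpoint is secondary, and nothing is decided on it. All of that stands. Section 14.0 also concedes, for the response-rate comparison, that "this sample size may not have enough power to distinguish the two arms", so nobody is promised a powered contrast between arms.

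It is also fair that the gain rests on assumed inputs. At 0.5 SD and rho 0.3-0.5 it is only about 2 to 6 percentage points, and both tests remain badly underpowered. Ties at the scale floor shrink the gain further. The large gains need a high correlation and a large effect. Against that, the change costs almost nothing, and at 15 per arm nothing measurable is lost even at rho 0.

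Missing second scores are a real limit, since Section 13.0 says "If at any time, the patient develops clinically significant progressive disease, s/he will be withdrawn from the study". But baseline is required before registration, so incomplete pairs arise mainly from a missing week-16 score, which the planned test needs as well.

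Two stronger readings are tempting. A reader might infer that objective 3 has no analysis of change. The documents do not support that: per-arm trends over two time points are the change from baseline, and asking for an interval is a reporting preference. A reader might also count eight tests (four scores at two times) and charge the plan with a stated multiplicity problem. The count is an inference, because the test sentence gives no number, and the plan attaches no action to any of these tests.

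**Conclusion.** The point holds as a low-cost improvement to a secondary comparison. Read literally, Section 14.0 tests baseline scores, which cannot inform on treatment, and ignores those scores at week 16, where they could help.

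The benefit ranges from about nil (rho 0) to about 25 percentage points of power (rho 0.7, 0.8 SD, 15 per arm, normal scores). At rho 0.5 it is about 11 points for 0.8 SD and 6 for 0.5 SD. These sizes depend on a correlation, an effect and a score distribution that the documents do not give.

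A reader might infer that the week-16 result would be biased or its type I error inflated. It would not be: averaged over randomisations the error rate is 0.04-0.05, and the higher rejection rates in step 6 apply only to trials that happen to be imbalanced at baseline.

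**What to change.** In Section 14.0, replace the rank-sum tests at both time points with one prespecified between-arm comparison of the week-16/end-of-treatment total and subscale scores by rank ANCOVA. Rank the baseline and the later scores across both arms, then test arm adjusting for baseline rank. Name this as the test and do not switch method after seeing the data. The disease-type stratum used in randomisation may be added if the strata are large enough. Summarise baseline scores by arm without a test.

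Optionally, report each arm's paired change with a 95% CI, and the number of patients with both scores. The half-width is t(n-1) × sqrt(2(1 - rho)/n), assuming equal SDs at both times: about 0.66/0.55/0.43 SD at 15 patients and 0.91/0.77/0.60 SD at 9, for rho 0.3/0.5/0.7. Any baseline-adjusted mean difference should be labelled descriptive. At 15 per arm its simulated 95% CI covers 0.95 with normal scores but only 0.89-0.91 with lognormal ones, and it can disagree with the rank test.

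Cost: wording, one degree of freedom, and the need for both scores from each patient. No new data, visits or patients are required.

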**Secondary Objectives:**

1. To assess the clinical efficacy of Talimogene Laherparepvec with or without radiotherapy in patients with cutaneous metastases from melanoma, Merkel cell carcinoma, or other solid tumor malignancy. Clinical efficacy will be measured by determining the objective response rate (ORR) defined as patients achieving complete response or partial response defined by the modified World Health Organization (mWHO) criteria. Response will be assessed approximately 16 weeks after the first treatment. Among patients randomized to receive Talimogene Laherparepvec, we expect ORRs to be comparable to previous studies (26.4% 95% CI 21.4-31.5%). Patients randomized to receive Talimogene Laherparepvec and radiotherapy are expected to have ORRs higher than previously published studies of Talimogene Laherparepvec alone.
2. To assess the safety of Talimogene Laherparepvec with or without radiotherapy in patients with cutaneous metastases from melanoma, Merkel cell carcinoma, or other solid tumor malignancy as measured by the frequency of adverse events (grade 2-5 adverse events). The window for adverse event assessment will include the 20 week time period from first treatment until 5 weeks after last treatment. We expect that frequency and grade of adverse events in patients receiving Talimogene Laherparepvec will be similar to previous studies of Talimogene Laherparepvec alone, and that radiotherapy will increase the frequency and grade of adverse events.
3. To evaluate the patient reported quality of life following Talimogene Laherparepvec with or without radiotherapy in patients with cutaneous metastases from melanoma, Merkel cell carcinoma, or other solid tumor malignancies treated with Talimogene Laherparepvec with or without hypofractionated radiotherapy. It is expected that quality of life (described further in section 12.0) will improve after Talimogene Laherparepvec with or without radiotherapy.
4. To assess the duration of response (DOR) in patients achieving a partial or complete response. DOR will be defined as the duration of time from occurrence of partial or complete response until first occurrence of progression or date of death if the patient dies due to any causes before progression.

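### The planned log-rank comparison of duration of response uses responders only, so it is not a randomised comparison, and it would rest on roughly four to eight patients per arm.

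*Combined protocol and SAP*

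**What the plan says.** Secondary objective 4 in Section 2.0 is "To assess the duration of response (DOR) in patients achieving a partial or complete response". The clock starts at response: "DOR will be defined as the duration of time from occurrence of partial or complete response until first occurrence of progression", with death from any cause before progression also counted as an event.

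The analysis is set out in Section 14.0: "DOR will be assessed using actuarial curves based on patients who achieved response and compared between the two arms using a stratified log-rank test". The sentence that follows bases time to response onset, progression-free survival (PFS) and overall survival (OS) on all patients. DOR is thus the only time-to-event comparison restricted to a subgroup defined by outcome. The same paragraph says the immunologic data will be summarised descriptively; it puts no such label on the DOR comparison.

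The size of each arm comes from the two-stage design: "In the first stage, 9 evaluable patients will be accrued to each arm", and if at least one of them responds, "then an additional 6 patients will be accrued to that arm in the second stage". That makes at most 15 evaluable patients per arm. For objective response, secondary objective 1 expects 26.4% (95% CI 21.4–31.5%) with talimogene laherparepvec alone and a higher rate, with no figure given, when radiotherapy is added. No event count, effect size, significance level or power is stated for DOR.

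**The concern.** Randomisation makes the arms comparable at entry. It does not make the responders in one arm comparable with the responders in the other when treatment affects who responds. If radiotherapy turns patients with a poorer outlook into responders, Arm A's average DOR can fall even though nobody is harmed. If the extra responders happen to have more durable disease control, DOR can look longer without any effect on durability. The observed durations cannot separate these explanations from a treatment effect, and a larger sample would not remove the problem.

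The small numbers add a second difficulty: the test has little chance of detecting even a large difference, and its usual chi-square approximation is poor. What is at stake is the reading of one secondary result. A reported log-rank p-value invites a causal interpretation that the comparison cannot carry.

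**Working it through.** **1. The plan's own design figures.** The rule is to stop an arm with 0 responses in 9, and otherwise require 3 or more of 15. Exact binomial calculation at response rates of 7.5% and 27% gives:
- type I error 0.094, against a limit of 0.10;
- power 0.802, against 0.80;
- early stopping probability 0.496 and 0.059, against the stated 0.50 and 0.06.

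The design reproduces, so 15 evaluable patients per arm is a sound basis for what follows.

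**2. Expected responders at full accrual (15 × response rate).**

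| Arm | Rate | Source of rate | Responders |
|---|---|---|---|
| B | 26.4% | Section 2.0 | 3.96 |
| B | 21.4–31.5% | its confidence interval | 3.2–4.7 |
| either | 27% | design rate, Section 14.0 | 4.05 |
| A | 35–50% | assumption; no figure in the protocol | 5.3–7.5 |

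The 27% row borrows a rate set for the primary systemic response, not for objective response. An arm closed after the first stage could have few responders or none.

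**3. Power.** Assumptions: two-sided 0.05, equal groups, every responder has an event. Schoenfeld's formula is power = Φ(√(d/4) × |ln HR| − 1.96), where d is the number of events.
- d = 8, HR 0.50: Φ(1.414 × 0.693 − 1.96) = Φ(−0.98) = 0.16.
- d = 8, HR 0.33: 0.35.
- d = 12, HR 0.50: 0.22.
- HR needed for 80% power with d = 8: exp(−2.80/1.414) = 0.14.
- Events needed for 80% power at HR 0.50: 4 × 2.80² / 0.693² ≈ 65.3, so 66.

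A simulation of 10,000 trials with 4 against 4 responders at HR 0.50 gives 13% unstratified and 12% when responders fall at random into three strata. Eight events is the best case for 4 against 4. The only scheduled PET/CT after baseline is at week 16 or end of treatment (Section 10.0), and the follow-up visit in Section 9.0 lists adverse event review only.

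**4. Reliability of the p-value.** Assume 4 against 4 responders split 2+2, 1+1 and 1+1 over three strata, with no censoring. There are C(4,2) × C(2,1) × C(2,1) = 24 equally likely orderings under the null hypothesis. Complete separation gives:
- 2+2 stratum: O − E = 2 − (1/2 + 1/3) = 1.167; variance 1/4 + 2/9 = 0.472.
- Each 1+1 stratum: O − E = 0.5; variance 0.25.
- Total: 2.167² / 0.972 = 4.83, nominal p = 0.028.

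Two of the 24 orderings are this extreme, so the exact p is 2/24 = 0.083. They are the only two with nominal p below 0.05. In this split a nominal 5% test therefore has a true size of 8.3%.

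**5. Size of the selection effect (illustration only).** Let an unobserved prognostic factor drive both response and DOR, with a log-hazard slope of 0.5 to 1.0, and let treatment have no effect on DOR. If radiotherapy raises the response rate from 26.4% to an assumed 40%, Arm A's median DOR among responders is 0.87 to 0.75 times Arm B's. With equal response rates the ratio is 1.0. Reversing the sign of the slope would reverse the direction.

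**The case against.** Four objections deserve weight.

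**No conclusion hangs on DOR.** A reader might infer that the trial means to draw a treatment conclusion from this test. The protocol says no such thing. An arm is taken forward on response counts, "if 3 or more patients achieve response out of 15 then that treatment arm will be considered worthy of further investigation", and if both qualify the one with the higher observed response rate is preferred. This stands and limits the importance of the point.

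**Significance is attainable.** It is tempting to say that 0.05 cannot be reached with so few responders. That holds only for an exact test in the split above. Section 14.0 names a stratified log-rank test and no exact version, and the usual chi-square form reaches 0.028 there. Unstratified, 4 against 4 with complete separation gives chi-square 7.34 and p = 0.007. The defensible criticisms are low power and an unreliable p-value.

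**The counts and strata are assumptions.** About four responders fits Arm B and should not be asserted for Arm A, where more are expected. Halving 26.4% to about 13%, by analogy with the Section 3.0 argument about uninjected metastases, gives about two responders, but the protocol states no such rate for objective response. Randomisation is stratified by disease type, yet neither the number of levels nor the strata of the log-rank test are given. A 3+3 and 1+1 split has an exact floor of 2/40 = 0.05.

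**The limitation is partly conceded.** Section 14.0 admits that the sample may be too small to distinguish the arms. It does so for the response-rate comparison only, and a caveat about power would not address selection on response.

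**Conclusion.** The point holds as a minor flaw in a secondary analysis. The DOR test conditions on a post-randomisation outcome that the protocol itself expects to differ between arms, and nothing labels it descriptive. That part rests on the protocol's text and needs no numerical assumption.

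The sizes do rest on assumptions: full accrual of 15 evaluable patients per arm, a 26.4% response rate in Arm B, 35–50% in Arm A, two-sided 0.05, HR 0.50 and every responder having an event. Under the 4-against-4 case, power is about 12–16%. The gap between nominal 0.028 and exact 0.083 belongs to one assumed split. The direction of the selection bias is unknown, and the ratios of 0.75–0.87 show only that it could be material. The primary endpoint, the two-stage rule and arm selection are unaffected.

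**What to change.** In Section 14.0, remove the between-arm log-rank test for DOR, or keep it labelled exploratory with no inferential p-value. Report DOR by arm as description: each responder's duration and censoring status, with the actuarial curves already planned. Rest between-arm time-to-event comparisons on endpoints the plan analyses in all patients, namely PFS and OS. Response should not be cited as an endpoint in all randomised patients, because Sections 12.0 and 14.0 assess the primary response in evaluable patients and replace those who are not evaluable.

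The cost is a change to one sentence and the loss of one secondary p-value. Data collection, sample size and the primary decision rule stay as they are.
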